Diaphragmatic weakness is considered to be the major reason contributing to the reduction of lung function of people after stroke [11]. Diaphragm, as the primary inspiratory muscle, accounts for approximately 75% of the airflow into the lungs during quiet breathing [12]. However, most people after stroke have diaphragmatic weakness due to the loss of central motor control, leading to paralysis of the diaphragm in the contralateral side [13, 14]. Diaphragmatic weakness can lead to asymmetric respiratory chest movements, changes in the respiratory mechanism, and consequently reduced lung function [11, 14, 15]. The thickness of the affected diaphragm of patients after subacute and chronic stroke was found only to have nearly 50% of those of healthy individuals [13]. Contraction of diaphragm fibers can be quantified by the diaphragmic thickening fraction (DTF), determined by “(thickness of the diaphragm at end inspiratory - thickness at end expiratory)/thickness at end expiratory” [16]. A reduction in diaphragmatic contraction was reported to be significantly correlated with decreased lung function (e.g. FVC, FEV1, MIP, PEF) in people after stroke [13, 17].

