The inclusion criteria are: (1) age \geq 18 years; (2) clinically diagnosed with ischemic and/or hemorrhagic stroke; (3) duration of stroke range from 1 month to 12 months after diagnosis; (4) had no facial palsy, which could prevent proper labial occlusion; (5) had not undergone thoracic or abdominal surgery; (6) could understand and follow the verbal instruction; (7) stable cardiac conditions; (8) no previous history of respiratory problems.

The exclusion criteria are: (1) acute myocardial infarction or acute heart failure; (2) acute pain on chest or abdominal; (3) with the clinical signs of significant pulmonary disease; (4) consciousness impaired; (5) patient with nasal feeding tube, tracheal tube and/or any condition, which prevent the measurement or training.

Recruitment of healthy participants:

The inclusion criteria are: (1) age ≥ 18 years; (2) had not undergone thoracic or abdominal surgery; (3) no previous history of respiratory problems.

The exclusion criteria are: (1) acute myocardial infarction or acute heart failure; (2) acute pain in the chest or abdominal; (3) with the clinical signs of significant pulmonary disease; (4) unstable hypertension, arrhythmias, or unstable cardiovascular conditions, such as fluctuations in blood pressure and heart rate, indicate poor cardiac prognosis or the need for vasopressor medications; (5) pregnant.

Ethical approval:

Ethical approval will be sought from the Research Ethics Committee of Hong Kong Metropolitan University and Shenzhen Second People's Hospital.

Sample size calculation:

Sample size calculation will be based on the use of repeated-measures analysis of variance (ANOVA) using the G*Power 3.1. Considering an effect size of 0.2, an alpha error probability of 0.05 and a power of 0.80, the estimated sample size is 54 participants. An additional 20% of the sample size will be included to account for attrition. The final estimated sample size will be at least 130 participants (65 for each cohort).

Procedure:

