The nature of the study will be explained to the participants and written informed consent will be obtained. Demographic data of each participant including age, sex, height, weight, BMI, percent body fat, lean body mass, and smoking history will be recorded. For people after stroke, the stroke type (cerebral infarction, intracerebral hemorrhage), medical history (hypertension, diabetes mellitus, cardiovascular disease, lipidemia, kidney disease) will also be recorded. The National Institutes of Health Stroke Scale (NIHSS), Modified Rivermead Mobility Index (MRMI), Modified Rankin Scale (mRS), Barthel index (BI) will be retrieved from the patient's medical record.

Participants will be invited to attend the cardiopulmonary laboratory of the hospital at a time > 2 hours after a light meal. Participants are requested to avoid caffeine-containing products, nicotine, alcohol and vigorous exercise for at least 12 hours before attending the laboratory.

Each participant will be asked to perform the lung function test to measure the FVC, FEV₁, and MIP after including the study. After completing the baseline lung function test, participant will be required to sit on the chair and rest for 15 minutes, after that, two trained researchers will use two identical ultrasonography to measure the left and right diaphragmatic thickness simultaneously at quiet breathing, the end of tidal inspiratory and the end of tidal expiratory, respectively. 3 ultrasonic images will be captured to calculate the mean diaphragmatic thickness of each breathing status. In order to determine the inter-rater reliability of the measurement of ultrasonography of

those two trained researchers, 20 participants will be chosen out randomly to receive twice diaphragmatic thickness measurement at quiet breathing, the end of tidal inspiratory and the end of tidal expiratory. However, during the second measurement, those two trained researchers will change their position to measure the contralateral side diaphragmatic thickness independently.

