After the baseline measurement, all participants will be requested to use a nose clip to hold the nose and breathe with the mouth through a pressure threshold inspiratory loading device (POWERbreathe, KH2, England). The inspiratory pressure will be set at 30%, 40%, 50%, 60%, 70%, or 80% of their MIP, in random order. Each MIP intensity protocol consists of 10 breaths. The procedure of IMT is followed by the published research protocols in people after stroke [28]. All MIP intensity protocols will be conducted in one day. A period of at least 10 minutes of rest time will be allowed between different protocols of contraction intensity (% MIP) on the same day [29].

Thickness of the left and right diaphragm (stroke and non-stroke), will be measured simultaneously by two identical ultrasonography at the end of maximum inspiration of 10 breaths of each MIP intensity protocol. The diaphragm thickness of both the left and right diaphragm at the end inspiratory breaths of the 10 breaths of each MIP intensity protocol will be recorded. Surface electromyography (sEMG) will be used to measure the activity of accessory muscle (sternocleidomastoid muscles) during each MIP intensity protocol. The % of MIP that associates with the highest calculated DTF and a relatively stable change in the activity of accessory muscles will be considered an appropriate training intensity for further IMT protocols.

The self-perceived exertion level will also be determined by the Rate of Perceived Exertion Borg scale at the end of each MIP intensity protocol [30].

All research procedures will be repeated again after 2 days to examine the test-retest reliability of ultrasonographic measurements of DTF.

Outcome measures:

[figure not shown]
Lung function

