Though various measures will be taken to minimize the risk of adverse event throughout the study, any adverse events that might happen will be recorded.

Statistical analysis:

All data will be reported as mean \pm standard deviation (SD) unless otherwise indicated. Demographic data and clinical characteristics for all participants will be summarized using descriptive statistics. Repeated-measures ANOVA will be used to compare the differences of DTF and sEMG parameters determined at each inspiratory pressure separately. Intraclass correlation coefficient will be used to determine the inter-rater reliability of two ultrasonic operators and examine the test-retest reliability coefficient of ultrasonographic measurements of DTF recorded with different inspiratory pressures.

P value will be set at 0.05. All data will be analyzed using the IBM SPSS Statistics for Windows, Version 25.0 (Armonk, NY: IBM Corp).

References:

1. Gbd, S., Global, regional, and national burden of stroke and its risk factors, 1990-2019: a systematic analysis for the Global Burden of Disease Study 2019. *Lancet Neurol*, 2021. 20(10): p. 795-820.
2. Wu, X., et al., The hospital costs of stroke patients in Chinese island populations: an 11-year tendency analysis. *J Stroke Cerebrovasc Dis*, 2015. 24(5): p. 988-992.
3. Feigin, V., et al., Global, Regional, and Country-Specific Lifetime Risks of Stroke, 1990 and 2016. *N Engl J Med*, 2018. 379(25): p. 2429-2437.
4. Li X and Z. X., Annual data set on national mortality surveillance 2018. Beijing: China Science and Technology Press, 2019.
5. Menezes, K.K., et al., Respiratory muscle training increases respiratory muscle strength and reduces respiratory complications after stroke: a systematic review. *J PHYSIOTHER*, 2016. 62(3): p. 138-44.
6. Liu, X., et al., Assessment of Diaphragm in Hemiplegic Patients after Stroke with Ultrasound and Its Correlation of Extremity Motor and Balance Function. *Brain Sciences*, 2022. 12(7): p. 882.
7. Lista-Paz, A., et al., Pulmonary function in patients with chronic stroke compared with a control group of healthy people matched by age and sex. *Physiother Theory Pract*, 2022: p. 1-9.
8. Wilson, R., Mortality and cost of pneumonia after stroke for different risk groups. *J Stroke Cerebrovasc Dis*, 2012. 21(1): p. 61-67.
9. Saposnik, G., et al., Variables associated with 7-day, 30-day, and 1-year fatality after ischemic stroke. *Stroke*, 2008. 39(8): p. 2318-2324.

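### Both hemidiaphragms are measured at every load, but side has no defined role in the DTF analysis or in the choice of training load

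*Combined protocol and SAP*

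**What the plan says.** The Introduction builds the study on side-specific weakness. It describes paralysis of the hemidiaphragm opposite the lesion and reports that the affected diaphragm's thickness "was found only to have nearly 50% of those of healthy individuals". The Procedure follows this through in the measurements: "Thickness of the left and right diaphragm (stroke and non-stroke" is the description of what is imaged at each of the six loads (30% to 80% of MIP). The Figure 1 captions also label one side as the stroke side and the other as the non-stroke side.

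The Statistical analysis section does not follow it through. It says: "Repeated-measures ANOVA will be used to compare the differences of DTF and sEMG parameters determined at each inspiratory pressure separately". There is no side factor, no side-by-load term, and no rule for reducing two DTF values per load to one. The stroke variables listed in the Procedure are stroke type, medical history and four scales; side of lesion or hemiplegia is not listed. The aim asks for the strongest thickening fraction in people after stroke, and the selection rule in the Procedure asks for the load with the highest DTF together with fairly stable accessory-muscle activity. Neither names a side.

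On operators, "two trained researchers will use two identical ultrasonography to measure the left and right diaphragmatic thickness simultaneously". In 20 randomly chosen participants the measurement is repeated and "those two trained researchers will change their position to measure the contralateral side"; that repeat covers quiet and tidal breathing only.

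**The concern.** The study's product is a decision: one training load for later protocols. Each patient contributes two correlated DTF curves, and the background gives reason to expect them to differ. An analysis with load as its only factor cannot say whether they do.

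The selection rule is then incomplete. If, hypothetically, the affected side peaked at 50% of MIP and the unaffected side at 70%, the plan would not say which load wins. An analyst could use the affected side, the unaffected side, left, right, the mean or the better side, and could choose after seeing the curves. The answer could depend on that choice.

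If hemiplegic side is not captured in the dataset, the options narrow to left, right or the mean. Each of these mixes affected and unaffected muscle when both left and right hemiplegia are enrolled.

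**Working it through.** **1. The plan's own figure.** The Sample size calculation says: "Considering an effect size of 0.2, an alpha error probability of 0.05 and a power of 0.80, the estimated sample size is 54 participants". It then says "An additional 20% of the sample size will be included to account for attrition", and "The final estimated sample size will be at least 130 participants (65 for each cohort". The last steps reproduce: 54 × 1.2 = 64.8, rounded up to 65, and 2 × 65 = 130.

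For the 54, take f as Cohen's f, N participants, m = 6 loads, correlation ρ between loads, one group and sphericity. The within-person test has noncentrality λ = N·m·f²/(1 − ρ), with df1 = m − 1 and df2 = (N − 1)(m − 1).
- At ρ = 0, N = 54: λ = 54 × 6 × 0.04 = 12.96, power 0.795. N = 55 gives 0.804, so this setting comes within one participant of 54.
- At ρ = 0.5, N = 28 is already enough (power 0.803).
- A within-between interaction entered with 6 groups, 6 measurements and ρ = 0.5 gives exactly 54.

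The plan states none of these settings. None contains a side term with two levels.

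**2. If a fixed body side (left or right) were analysed.** Assumptions, none given in the documents: affected-side load effect f = 0.2; unaffected-side effect r times that, with the same profile over loads; half the patients with left and half with right hemiplegia; n = 65. Extra variance from mixing the two kinds of curve is ignored. The average effect on a body-side curve is f = 0.2 × (1 + r)/2. With df = 5 and 320, λ = 390f² at ρ = 0 and 780f² at ρ = 0.5.

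| r | f | λ, ρ = 0 | Power, ρ = 0 | λ, ρ = 0.5 | Power, ρ = 0.5 |
|---|---|---|---|---|---|
| 0 | 0.10 | 3.9 | 0.28 | 7.8 | 0.54 |
| 0.5 | 0.15 | 8.775 | 0.60 | 17.55 | 0.915 |
| 1 | 0.20 | 15.6 | 0.875 | 31.2 | 0.996 |
| 1.5 | 0.25 | 24.375 | 0.98 | 48.75 | >0.99 |

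The r = 1 row is also the power of an affected-side analysis. At n = 54 and ρ = 0 the four powers are 0.23, 0.51, 0.795 and 0.95.

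**3. If the two sides were averaged.** Averaging also removes noise. With between-side residual correlation c, f = [0.2 × (1 + r)/2] / √((1 + c)/2). At n = 65, for c from 0.8 down to 0:

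| r | Power, ρ = 0 | Power, ρ = 0.5 |
|---|---|---|
| 0 | 0.31 to 0.54 | 0.60 to 0.875 |
| 0.5 | 0.66 to 0.915 | 0.94 to 0.999 |
| 1 | 0.91 to 0.996 | 0.998 or more |
| 1.5 | 0.99 or more | >0.99 |

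The comparators are 0.875 and 0.996 for the affected side alone. At r = 0.5, ρ = 0 and c = 0, averaging raises power from 0.875 to 0.915.

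**4. The interaction test.** On affected-minus-unaffected differences, f = 0.2 × |1 − r| / √(2(1 − c)). At n = 65, ρ = 0.5 and c from 0 to 0.8, power is 0.875 to nearly 1 for r = 0, and 0.28 to 0.94 for r = 0.5 or 1.5. At ρ = 0 the ranges are 0.54 to nearly 1, and 0.15 to 0.66.

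**5. Operators.** The two operators scan opposite sides at the same time, so operator and side are confounded within a session. A DTF offset that is constant over loads cancels from a comparison of loads within one side, which is the comparison planned. A constant thickness offset does not cancel fully, because DTF divides by end-expiratory thickness: it rescales a participant's curve but does not move its peak. For a side contrast, if each operator kept one body side throughout, a DTF offset d would bias the healthy left-right difference by d. It would bias the affected-unaffected difference by d(0.6 − 0.4) = 0.2d at a 60:40 split of hemiplegic side.

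**The case against.** A reader might infer that the plan dilutes the affected-side response and loses power for it. The documents do not support that. They nowhere say that DTF will be averaged or analysed by left and right, and the only clinical side labels they use are stroke and non-stroke. Curves run by those labels would have no dilution. The direction is also open. If weakness of the affected side means that the unaffected side responds at least as much, r is 1 or more and a body-side curve loses no power; the risk is then that a weak affected-side response is masked or overstated.

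A reader might also infer that the affected side is what the study asks about. The aim names no side, so interest in the affected side is implied only by the background and the labels.

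Nor does the text establish that each operator is tied to one body side. Simultaneous scanning is stated; a fixed assignment across participants is not. An operator offset matters mainly for a side contrast, which the plan does not currently contain.

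Finally, both sides are imaged at every load, so the images could support a side analysis. That stands, provided hemiplegic side is captured. It does not answer the omission: the analysis has no side term, the list of variables does not secure the side, and the selection rule does not say which curve it reads.

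**Conclusion.** The point holds as an omission in the analysis plan. The role of side is unspecified. The one-factor ANOVA cannot test whether the load response differs by side, and the selection rule has no single answer if the sides peak at different loads. These conclusions follow from the text and need no numerical assumption.

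Any effect on power is conditional. For a body-side curve it runs from a severe loss (0.28 against 0.875 at r = 0, ρ = 0) through no loss at r = 1 to a gain (0.98) at r = 1.5. These figures rest on assumed values of r, ρ and the side split, and on f = 0.2 applying to the affected side. They also assume that both sides share one profile over loads, so they say nothing about differing peaks. The operator issue is secondary and becomes relevant once a side contrast is added. The change is worth making because the images are already planned and the cost is small.

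**What to change.** - Add side of hemiplegia to the recorded stroke variables.
- In the stroke cohort, replace the one-factor ANOVA for DTF with a within-person side (affected/unaffected) by load (six levels) model. Report the interaction and both side-specific curves with confidence intervals. Given the power in step 4, a non-significant interaction should not be read as showing that the sides respond alike.
- State before data are seen which side's curve feeds the selection rule. The aim leaves this open, so the investigators must decide it. State also how side is handled in controls.
- Alternate the two operators between left and right across participants, fixed within a participant over all loads and both sessions; failing that, log operator by side.

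The cost is one data field, one extra model factor, a few sentences in the analysis section, and operators who must be able to work on either side. No additional measurements are needed.

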Inspiratory muscle training (IMT) is an intervention designed for improvement of inspiratory muscle (including the diaphragm) strength and endurance in healthy adults and patients suffering from different diseases (e.g. Parkinson, chronic obstructive pulmonary disease, cardiovascular disease) [18-21]. Regarding the IMT training protocol, the commonly reported training intensities varied between 30-80% of MIP in people after stroke [22-24]. Although the diaphragm is the primary inspiratory muscle, the use of IMT may not help improve the diaphragmatic contraction under some circumstances. Previous studies suggested that, in healthy adults and people receiving mechanical ventilation, when inspiratory load exceeds the capacity of the diaphragm (higher than 60% MIP), the accessory respiratory muscle (in particular the sternocleidomastoid muscle) would be activated dramatically, which would increase work of breathing and fatigue [25, 26]. Other studies also reported that high IMT intensity may have the risk to increase the work of breathing thereby leading to fatigue [27] or resulting in a decrease, rather than increase, in surface electromyography signals in diaphragmatic activity [27]. It is postulated that IMT recruits accessory muscles such as sternocleidomastoid rather than diaphragm during the practice [24]. Hence, evaluation of effectiveness of IMT on DTF in people after stroke and further investigation on determining an optimal training protocol including inspiratory effort and training intensity for recruiting diaphragmatic activities in the stroke population are warranted.

Aims of the study:

To determine the optimal training intensity that is associated with the strongest diaphragmic thickening fraction in people after stroke.

Project significance:

Outcomes of this project study will fill the existing knowledge gaps in the understanding of the relationship between inspiratory pressure and recruitment of diaphragmatic muscles in people after sub-acute and chronic stroke.

4. Research methodology

Study design:

This study will be a cross-sectional study.

Participants:

Individuals who have had a stroke and healthy adults will be invited to participate in this study.

Participants recruitment for people after stroke:

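### Does choosing the load with the highest DTF require an end-expiratory thickness measured at every load, when the plan describes one only at rest?

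*Combined protocol and SAP*

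**What the plan says.** The aim (section 3, Aims of the study) is "To determine the optimal training intensity that is associated with the strongest diaphragmic thickening fraction in people after stroke". The Introduction defines DTF as the ratio "thickness of the diaphragm at end inspiratory - thickness at end expiratory)/thickness at end expiratory", without saying whether the end-expiratory value is taken at rest or under load.

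The Procedure (section 4) describes two imaging occasions:

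- **At rest, before any load:** both sides are imaged "at quiet breathing, the end of tidal inspiratory and the end of tidal expiratory, respectively", and "3 ultrasonic images will be captured to calculate the mean diaphragmatic thickness of each breathing status".
- **Under each of the six loads (30% to 80% of MIP, in random order):** thickness "will be measured simultaneously by two identical ultrasonography at the end of maximum inspiration of 10 breaths of each MIP intensity protocol". The next sentence, on both sides of the diaphragm, says that thickness "at the end inspiratory breaths of the 10 breaths of each MIP intensity protocol will be recorded". Neither sentence mentions end-expiration.

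Between loads, "A period of at least 10 minutes of rest time will be allowed between different protocols of contraction intensity". The selection rule is "The % of MIP that associates with the highest calculated DTF and a relatively stable change in the activity of accessory muscles". The Statistical analysis section compares DTF across pressures by repeated-measures ANOVA and names no denominator. The legends to Figure 1(b) and (c) pair an image at the end of tidal expiration with one at maximum inspiration at 30% MIP. The flow chart and the figure under Outcome measures cannot be read in the copy reviewed.

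**The concern.** DTF is both the subject of the aim and half of the rule for choosing an intensity, yet its denominator at each load is not stated. If one resting value serves all six loads, then for one person and one side, ranking loads by DTF is the same as ranking them by end-inspiratory thickness. Should end-expiratory thickness itself change with load, that change would enter DTF as if it were contraction, and no other planned measurement would reveal it. At stake is whether the load with the highest DTF is the one at which the diaphragm thickens most within the breath, or the one at which its starting thickness has moved.

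**Working it through.** **1. Which denominator does the text produce?** DTF needs an end-expiratory thickness. The only one whose collection is described is the resting mean of three images. Under load only end-inspiration is recorded. The Figure 1 legends use the word tidal, which the Procedure uses for the resting images. The legend could also mean that both images came from the 30% protocol, so it is supporting evidence rather than proof. An analyst working from these data has one value to divide by: the resting one.

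**2. What would a shift do?** Let T0 be resting end-expiratory thickness, D the within-breath DTF at a load, and x the relative end-expiratory shift at that load. End-inspiratory thickness is T0(1+x)(1+D). With the resting denominator the computed DTF is (1+D)(1+x) − 1, which exceeds D by (1+D)x. A shift common to all loads multiplies every 1+D by the same factor and changes no ranks.

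**3. How large must it be?** The documents give neither DTF by load nor any x. Assume load A has DTF 65% and load B 60%.

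- Shift at one load only: 0.05/1.60 = 3.1% at B, or 0.05/1.65 = 3.0% (downward) at A.
- Shift growing linearly from zero at 30% MIP to s at 80% MIP: x = s·k/5, with k = 0 to 5. The order reverses at s = 0.05 / {[1.60·k(B) − 1.65·k(A)]/5}.

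| Loads compared | Size of s that reverses 65% v 60% |
|---|---|
| Adjacent | 13.5–17.9% |
| Two steps apart | 7.2–8.2% |
| Three steps apart | 5.0–5.3% |
| 30% v 80% MIP | 3.0–3.1% |

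For adjacent loads with other gaps, 62% v 60% needs 5.9–6.6% and 70% v 60% needs 23.8–41.7%.

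**4. A whole profile.** Take assumed DTFs of 0.40, 0.48, 0.55, 0.52, 0.47 and 0.42 from 30% to 80% MIP. With a linear shift of +10% at 80% MIP, the values at 50% and 60% MIP become 1.55 × 1.04 − 1 = 0.612 and 1.52 × 1.06 − 1 = 0.611, so 50% MIP is still highest. At +15% they become 1.55 × 1.06 − 1 = 0.643 and 1.52 × 1.09 − 1 = 0.657, and the maximum moves to 60% MIP. For shifts of −2% to −15% it stays at 50% MIP.

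**5. What would imaging end-expiration under load cost and gain?** Three frames × 6 loads × 2 sides = 36 readings per participant-session, against 10 × 6 × 2 = 120 end-inspiratory readings: +30%. For 130 participants in one session that is 36 × 130 = 4,680 readings; for the 65 stroke participants, 36 × 65 = 2,340.

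Error in the resting denominator scales all six of a person's 1+DTF values on one side alike and cannot reorder them. Error in a per-load denominator can. With an assumed frame CV c of 5–10% and DTF 60%:

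- SD added per person and load: 1.6c/√3 = 4.6–9.2 points.
- Contribution to the SE of a mean load difference in 65 people: 1.6c·√(2/3)/√65 = 0.8–1.6 points.

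I simulated cohorts of 65 with no shift at all and this denominator noise as the only random element. The selected load changed in about 18–46% of studies for a flat profile (60, 61, 62, 61, 60, 59%), about 1–19% with 2-point steps (58, 60, 62, 60, 58, 56%), and under 1% with 5-point steps.

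**The case for a change.** The best case for a change is this. An outcome that decides the result should be defined in full, and naming its denominator takes one sentence. End-expiratory frames not kept during the session cannot be recovered later. The repeat session after 2 days would not expose a load-driven shift, because one that recurs at the same load is reproducible and would leave the intraclass correlation high. A nearly flat DTF curve cannot be excluded, and there a shift of about 6% at 80% MIP is enough to reverse adjacent loads 2 points apart.

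All of that is correct as far as it goes. What stands is that the measure lacks a label and that the plan cannot test for a shift. What does not stand is the step from there to a faulty choice of load. That step needs a shift that differs between loads, and the documents offer no evidence of one. Several features work against it: the device resists inhalation only (Power Breathe section), each load lasts 10 breaths with a rest before the next, and random order keeps drift over time from being tied systematically to load. Nor would analysts diverge on the data described, since no loaded end-expiratory thickness is recorded for them to use. Imaging end-expiration under load also assumes the diaphragm stays visible at that point, which the plan does not state.

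**Conclusion.** No change to the plan is needed. The certain part is a missing label, which an analyst would fill in the only way the described data allow: DTF relative to resting end-expiratory thickness. That is a legitimate measure and answers the stated aim. If the unreadable flow chart or figure names a different denominator, the gap closes by another route.

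Extra imaging is a matter of design preference. It would add 30% to the readings to guard against a shift that the documents do not show. On the assumed 5-point gap, a smooth shift would have to reach 13.5% or more at 80% MIP before adjacent loads changed places. For widely separated loads or a nearly flat curve the threshold falls to about 3–7%, but in a flat curve a per-load denominator would by itself change the selected load in roughly 18–46% of studies with no shift present, so a disagreement could not be attributed to one. The thresholds rest on assumed DTF values, and the noise figures on an assumed frame CV of 5–10% with three frames per load. They also concern DTF alone, whereas the plan selects on DTF together with stable accessory muscle activity.

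### The plan names a training load without recording who completed the 10 breaths at it, so the named load may describe completers only

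*Combined protocol and SAP*

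**What the plan says.** The Procedure text in section 4 gives every participant six loads: "The inspiratory pressure will be set at 30%, 40%, 50%, 60%, 70%, or 80% of their MIP, in random order". The length of a block is fixed and short ("Each MIP intensity protocol consists of 10 breaths"), with at least 10 minutes of rest between loads. Diaphragm thickness is imaged at end-inspiration within each block, and sEMG is taken during it.

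The load to carry forward is then chosen on two criteria: "The % of MIP that associates with the highest calculated DTF and a relatively stable change in the activity of accessory muscles". Exertion is collected as well: "The self-perceived exertion level will also be determined by the Rate of Perceived Exertion Borg scale at the end of each MIP intensity protocol". Borg appears neither in the selection rule nor under Statistical analysis.

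The Statistical analysis text says "Repeated-measures ANOVA will be used to compare the differences of DTF and sEMG parameters determined at each inspiratory pressure separately". It names the package ("All data will be analyzed using the IBM SPSS Statistics for Windows, Version 25.0") but no analysis set and no method for missing blocks.

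Three other provisions come near the point:
- Stroke exclusion criterion 5 covers a "patient with nasal feeding tube, tracheal tube and/or any condition, which prevent the measurement or training". It applies at entry, not load by load.
- The sample size adds 20% for attrition in general.
- Adverse events are recorded but not linked to the choice of load.

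No available text defines a completed or stopped block, makes completion an outcome, or says how an unfinished block enters the DTF mean. The research flow chart is not shown and could not be checked.

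**The concern.** The plan itself gives some reason to expect difficulty at the heavier loads. The Introduction describes what happens "when inspiratory load exceeds the capacity of the diaphragm (higher than 60% MIP"): the sternocleidomastoid is strongly recruited, and work of breathing and fatigue increase. It also says that most people after stroke have diaphragmatic weakness. Two of the six loads, 70% and 80% MIP, lie above that mark.

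The result is meant to supply a training intensity for further protocols in people after stroke. If part of the cohort cannot finish a load, that fact bears directly on what the named load shows. The plan has no place to record it. The number of breaths completed and the reason for stopping cannot be reliably recovered after the session.

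**Working it through.** **1. The plan's own figure.** From the sample size text: 54 × 1.2 = 64.8, rounded up to 65 per cohort, and 65 × 2 = 130. This reproduces. The 20% is a general allowance, not one by load.

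**2. Numbers left if stoppers are dropped.** A conventional repeated-measures ANOVA needs all six loads from each participant. Let f be the share of the stroke cohort that misses at least one load. The documents give no value, so 10%, 20% and 30% are assumed.
- 65 × 0.9 = 58.5
- 65 × 0.8 = 52
- 65 × 0.7 = 45.5

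At f = 20% the whole attrition allowance is used before any ordinary dropout, and 52 is already below the 54 the plan set out to secure.

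**3. Whom the contrast describes when stoppers are dropped.** Let C be the completers' mean DTF change from a lighter to a heavier load. Let C − g be the change the stoppers would have shown.
- Whole cohort: (1 − f) × C + f × (C − g) = C − f × g
- Completers only: C
- Difference: f × g

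With g assumed at 20, 0 or −20 DTF points:

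| f | g = 20 | g = 0 | g = −20 |
|---|---|---|---|
| 10% | 2 | 0 | −2 |
| 20% | 4 | 0 | −4 |
| 30% | 6 | 0 | −6 |

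The shift is proportional to g, so halving g halves it. It favours the heavier load only when g is positive, that is, when stoppers would have responded less well there.

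**4. If the analyst instead averages whatever blocks exist.** The plan does not exclude this. Suppose the stoppers' DTF at the lighter load is d points below the completers'. The lighter-load mean then includes them and the heavier-load mean does not. The contrast becomes C + f × d, which differs from the whole-cohort value by f × (d + g). With f = 20%, d = 20 and g = 0, that is 4 points. A constant difference in level therefore cancels under complete-case analysis but not under simple available-block means. A mixed model uses the stoppers' lighter-load data and so can account for d. It cannot verify g, which is why a sensitivity analysis is needed.

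**5. Precision of a completion share at the planned size.** For 52 of 65, the Wilson 95% interval uses p = 0.8, n = 65, z = 1.96 and z² = 3.8416.
- Centre: (0.8 + 3.8416/130) / (1 + 3.8416/65) = 0.783
- Half-width: 1.96 × √(0.8 × 0.2/65 + 3.8416/(4 × 65²)) / (1 + 3.8416/65) = 0.096
- Interval: 0.687 to 0.879, or 69% to 88%

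Completion can thus be estimated usefully without adding participants.

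**The case against.** Several points on the other side are sound.

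- The Introduction's statement about loads above 60% MIP concerns healthy adults and ventilated people. It describes accessory-muscle recruitment and fatigue, not stopping within 10 breaths. The same section says that training intensities of 30-80% of MIP are commonly reported after stroke, a range that covers all six loads.
- Each load is scaled to the participant's own MIP, so a weak participant faces a lower absolute pressure. Short blocks, rest periods and the entry exclusion also limit failures. Failures may be few.
- The plan does not say that only completers are analysed or that partial blocks are discarded. It is silent, and thickness and sEMG are measured within the block, so partial data could be kept.
- The stated aim is physiological: the intensity with the strongest DTF.

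These points limit what can be claimed about frequency and size. They do not close the gap, because completion is still not recorded and the named analysis conventionally drops incomplete cases.

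A reader might go further and infer that stopping will fall on the 70% and 80% blocks, that the bias runs toward the heavier load, or that a probability of wrongly naming 80% MIP can be given. The documents support none of these. They give no stopping rate and no link between stopping and DTF response. The accessory-muscle criterion, which by the Introduction's reasoning would count against heavy loads, has no numerical definition, so the full rule cannot be simulated.

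**Conclusion.** The point holds as a conditional one. The selection rule does not consider completion, the plan does not record it, and the named ANOVA would conventionally remove participants who miss a load. If any stroke participants stop at a heavy load, the comparison and the named load describe completers, although the conclusion is worded for people after stroke.

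The failure rate, and the size and direction of any bias, cannot be derived from the documents. The shifts of up to 6 points in either direction rest wholly on assumed f and g, and they vanish if stoppers and completers respond alike. Even with no bias in DTF, the reader of the results would not know what share of the cohort could perform the named load. A reader might also infer that the rule needs a minimum completion share. That would be a judgement about tolerability that the documents neither make nor settle, and none is proposed here.

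**What to change.** **Procedure.** For each load and each session, record how many of the 10 breaths were completed and the reason for any stop. Take the Borg rating at the point of stopping. Keep the images and sEMG from breaths done before the stop.

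**Statistical analysis.** Replace the repeated-measures ANOVA for DTF and sEMG with a mixed model that uses all available blocks, so that a participant missing one load is not dropped. State in advance how partial blocks enter the model. Add a sensitivity analysis that varies the assumed DTF of non-completed blocks.

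**Reporting.** Show the completed share with its 95% CI, and Borg, by load and cohort beside mean DTF. State the named load together with its completion share. Where completion is not full, limit the conclusion to those who could complete that load.

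**Cost.** Two CRF fields per block, one extra table, and some added analysis work. No extra participants or procedures. The downside is that the conclusion may be narrower than the plan now intends.
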